### 8.3. Prohibited Concomitant Medications

#### 8.3.1. Prohibited Medications Throughout the Entire Study

The following medications cannot be administered for the specified times prior to the initiation of study IP and for the duration of the study.

- [REDACTED]
- Use of any cytotoxic/immunosuppressive agent including azathioprine, cyclophosphamide, methotrexate, mycophenolate mofetil, cyclosporine, oral corticosteroids whose dose exceeds > 12.5 mg/day (prednisone or equivalent).

*Note: Medications, such as prednisone (> 12.5 mg/day or equivalent), azathioprine, and cyclophosphamide can be initiated or increased at Investigator's discretion for the treatment of new or worsening shortness of breath (an exacerbation as described above [Section 8.1.2]).*

- Use of any cytokine modulators/biologics, such as etanercept, adalimumab, efalizumab, infliximab, or rituximab within 12 weeks of randomization.
- Use of any medications associated with hepatotoxicity risk, such as, but not limited to, acetaminophen > 3 grams/day and niacin > 2 grams/day while on study or within 2 weeks of first study dose.
- Use of marijuana within 3 months of Screening and during the study.

*Note: Drugs considered to be substrates of these transporters and without a narrow therapeutic index (eg, OATP1B1/3 substrates statins, OCT2 substrate metformin [Section 8.2.1]) should be closely monitored for potential drug interactions while subjects are participating in the study. Additional substrates of these transporters can be found in Appendix H.*

Exceptions may be made if, in the opinion of the Investigator, the medication [REDACTED] is needed to support best medical practice in the time frame of study participation AND such medication will not interfere with subject safety or the interpretation of study results. In such instances, the Sponsor's Medical Monitor and Investigator must concur.

### **8.3.2. Prohibited Medications During the 24-week Double-blind Placebo-controlled Treatment Phase**

The following medications cannot be administered for the specified times prior to the initiation of study IP and for the duration of the 24-week Double-blind Placebo-controlled Treatment Phase of the study. Subjects taking the following medications must adhere to the following minimum washout period:

- Medications to treat IPF/PPF including, but not limited to, [REDACTED]  
[REDACTED]  
D-penicillamine, endothelium receptor antagonists (eg, bosentan, ambrisentan), interferon gamma-1b, imatinib mesylate, and N-acetylcysteine [NAC], within 4 weeks prior to Screening Visit 1 and through Visit 9/Week 24.

### **8.4. Required Concomitant Medications**

There are no required concomitant medications for inclusion in this study. [REDACTED]  
[REDACTED]  
[REDACTED]

## 9. STATISTICAL CONSIDERATIONS

### 9.1. Overview

This is a double-blind, randomized, placebo-controlled study with two treatment arms of oral CC-90001 (200 mg or 400 mg PO QD), or one treatment arm in the PPF substudy, compared to placebo. This study consists of a 24-week Double-blind Placebo-controlled Treatment Phase, an 80-week Active Treatment Extension Phase, and a 4-week Post-treatment Observational Follow-up Phase. The primary efficacy analysis of percentage point difference in the percent predicted FVC at Week 24 and the secondary analyses will be performed after all IPF subjects complete the 24-week Double-blind Placebo-controlled Treatment Phase (Weeks 0 to 24) or terminate early prior to the Week 24 visit, and similarly but separately for the PPF subjects. Additional analyses will also be performed after the final database lock when all subjects complete the study or terminate early. This section outlines the statistical analysis strategy and details will be documented in a separate Statistical Analysis Plan (SAP) prior to unblinding of the treatment assignments for the 24-week Double-blind Placebo-controlled Treatment Phase of the study. The randomization schedule will be generated and implemented by the IWRS vendor.

### 9.2. Study Population Definitions

The safety population will include all randomized subjects who received at least one dose of IP. The analysis of safety data in this study will be based on the safety population and subjects will be included in the treatment group they actually received.

The Full Analysis Set (FAS) will include all randomized subjects who received at least one dose of IP. The analysis of efficacy data in this study will be primarily based on the FAS and subjects will be included in the treatment group to which they are randomized.

The Per Protocol (PP) population will include all randomized subjects who received at least one dose of IP, have Baseline (Visit 2) and at least one post-Baseline FVC evaluation, and have no important protocol deviation during the 24-week Double-blind Placebo-controlled Treatment Phase. The final determination of important protocol deviation criteria will be made prior to the unblinding of the database and will be separately documented.

The FAS and PP populations will be analyzed separately for the IPF study and the PPF substudy.

### 9.3. Sample Size and Power Considerations

The primary objective of the study is to estimate the effect of CC-90001 in subjects with IPF either not receiving SOC or currently receiving SOC.

Approximately 165 subjects (55 subjects for CC-90001 200 mg  $\pm$  SOC, 55 subjects for CC-90001 400 mg  $\pm$  SOC, and 55 subjects for placebo  $\pm$  SOC) provides 75% power for testing an overall difference of 2.2 percentage points in the Week 24 mean change from Baseline of percent predicted FVC value between either active treatment group  $\pm$  SOC and the placebo group  $\pm$  SOC (two-sided t-test;  $\alpha = 0.1$ ; standard deviation [SD] = 5%), assuming that approximately 45% of subjects will be receiving concurrent protocol-allowable SOC based on the projected enrollment. The group size estimate is based on an assumed treatment

difference of 3 in percent predicted FVC in the non-SOC cohort and 1.3 in percent predicted FVC in the SOC cohort at Week 24 from Baseline. The study will also estimate the effect of CC-90001 in the PPF cohort.

#### **9.4. Background and Demographic Characteristics**

Subject's age, height, weight, and baseline characteristics will be summarized using descriptive statistics, while sex, race and other categorical variables will be provided using frequency tabulations. Medical history data will be summarized using frequency tabulations by the Medical Dictionary for Regulatory Activities (MedDRA) system organ class and preferred term.

#### **9.5. Subject Disposition**

Subject disposition (analysis population allocation, entered, completed, discontinued, along with primary reason for discontinuation) will be summarized using frequency and percent by study phase. A summary of subjects enrolled by site will be provided. Protocol deviations will be summarized using frequency tabulations.

#### **9.6. Efficacy Analysis**

##### **9.6.1. Analysis of the Primary Efficacy Endpoint for the IPF Study**

A mixed-effect model of repeated measures (MMRM) will be used as the method for the primary efficacy analysis. The MMRM model will use the percent predicted FVC value as the dependent variable.

The MMRM model will include dose, time on treatment, current SOC (Yes/No), and interactions as fixed effects covariates. The model will also include the stratification factor applied to the non-SOC cohort, previous exposure to either pirfenidone or nintedanib (Yes/No), and Baseline percent predicted FVC value as fixed effects covariates. Time will be treated as a categorical variable in the MMRM model and will be considered as a repeated effect.

All post-baseline measurements up to Week 24 of percent predicted FVC values will be included in this analysis with no imputation of missing data other than that inherent in the MMRM model.

In addition to point estimates, 95% confidence intervals (CIs) for the differences calculated from the model (overall active treatment minus overall control, or active versus control within each cohort) of the least squares (LS) mean change from Baseline percent predicted FVC value and nominal p-values will also be provided, separately for each dose versus placebo comparison and also combining the 200 and 400 mg doses versus placebo comparison if both active treatment groups demonstrate efficacy. P-values and 95% CIs are considered descriptive measures of strength of association between dose and endpoint, rather than formal criteria to claim statistical significance.

In addition to the primary efficacy analysis of MMRM, non-parametric analysis of Rank-ANCOVA (Stokes, 2000) with a baseline FVC as a covariate for pair-wise comparisons with imputation of percent predicted FVC value for deaths to the worst rank will be applied as a

sensitivity analysis for the primary endpoint. Non-death discontinuation will be imputed in a different scheme; the details of the methods will be specified in the Statistical Analysis Plan.

To determine whether the treatment effect is consistent across various subgroups, the primary endpoint will be summarized by category of some classification variables observed at baseline including variables based on FVC (% predicted), age, time since first diagnosis of IPF, and prior therapy.

No multiplicity adjustment is planned for this study.

In addition to the above primary method of analysis on the primary endpoint, a Bayesian posterior probability that the effect ratios are greater than 1 (transformed on the log scale), within the naïve cohort and the SOC cohort separately, will be calculated using priors built from the current literature. The information from the literature may allow for a more precise estimate of the treatment effects.

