### **3.2. Study Duration for Subjects**

The study will have a total duration of up to 116 weeks. The study will consist of an up to 8-week Screening Phase; a 24-week Double-blind Placebo-controlled Treatment Phase; an 80-week Active Treatment Extension Phase; and a 4-week Post-treatment Observational Follow-up Phase.

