7. No features supporting an alternative diagnosis on transbronchial biopsy, bronchoalveolar lavage (BAL), or SLB, if performed prior to Screening
8. Percent predicted forced vital capacity (FVC)  $\geq 45\%$  and  $\leq 95\%$  at Screening confirmed by centralized review
9. Change in FVC (measured in milliliters [mL]) between Screening and Day 1 less than a 10% relative difference, calculated as: the absolute value of  $100\% * (\text{Screening FVC [mL]} - \text{Day 1 FVC [mL]}) / \text{Screening FVC (mL)}$
10. Hemoglobin-corrected percent predicted diffusion capacity of the lung for carbon monoxide ( $D_LCO$ )  $\geq 25\%$  and  $\leq 90\%$  predicted at Screening
11. Able to walk  $\geq 150$  meters during the 6-minute walk test (6MWT) at Screening
12. Females of childbearing potential (FCBP) must:
  - a. Have two negative pregnancy tests as verified by the Investigator prior to starting IP. She must agree to ongoing pregnancy testing during the course of the study, and after end of study treatment. This applies even if the subject practices true abstinence\* from heterosexual contact.

 A female of childbearing potential is a sexually mature female who 1) has not undergone a hysterectomy (the surgical removal of the uterus) or bilateral oophorectomy (the surgical removal of both ovaries) or 2) has not been postmenopausal for at least 24 consecutive months (that is, has had menses at any time during the preceding 24 consecutive months).

- b. Either commit to true abstinence\* from heterosexual contact (which must be reviewed on a monthly basis and source documented) or agree to use two effective birth control methods (one of which is highly effective) at the same time, and be able to comply with, effective contraception without interruption, 28 days prior to starting IP, during the study therapy (including dose interruptions), and for 28 days after discontinuation of IP.

Approved options for birth control are:

- Any one of the following highly effective methods: Hormonal contraception (for example, birth control pills, intravaginal ring, transdermal patch, injection, implant); intrauterine device (IUD); tubal ligation (tying your tubes); or a partner with a vasectomy.

*Note: Certain drugs may reduce the effectiveness of hormonal contraceptives during and up to one month after discontinuation of these concomitant therapies.*

- Any effective method, for example, condoms.

13. Male subjects must:

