**Table 5: Table of Events (Continued)**

	Screening Phase	24-Week Double-Blind Placebo-Controlled Treatment Phase			80-Week Active Treatment Extension Phase				Early Termination Visit	Post-Treatment Observational Follow-up
Visit(s) k	1 Screening	2 Baseline a	3	4-9 Every 4 Weeks	10E	11E-17E Every 4 Weeks	18E-25E Every 6 Weeks	26E End of Treatment		27E
Week(s)	-8 to -1	0	1 ± 3 days	4, 8, 12, 16, 20, 24 ± 3 days	25 ± 3 days	28, 32, 36, 40, 44, 48, 52 ± 3 days	58, 64, 70, 76, 82, 88, 94, 100 ± 3 days	104 ± 3 days		108 4-weeks post-treatment ± 3 days
INVESTIGATIONAL PRODUCT (IP)										
Dispense IP i	-	X	X	X	X	X	X	X j	-	-
Return and Count IP	-	-	X	X	X	X	X	X	X	-

Abbreviations: β-hCG = beta human chorionic gonadotropin; DLCO = diffusion capacity of the lung for carbon monoxide; E= Extension; ECG = electrocardiogram; FCBP= female of childbearing potential; HRCT = high resolution computed tomography; INR = international normalized ratio; IP = investigational product; IPF = idiopathic pulmonary fibrosis; [REDACTED] PT = prothrombin time; [REDACTED] [REDACTED] SGRQ = St.

George's Respiratory Questionnaire; 6MWT = Six-minute Walk Test; SpO2 = oxygen saturation; TB = tuberculosis; UCSD-SOBQ = University of California San Diego Shortness of Breath Questionnaire.

- a The Baseline value is defined as the last assessment prior to or on the date of the first dose of IP in the study.
- b PT and INR will only be done on those subjects who require monitoring for vitamin K antagonist levels (eg, warfarin).
- c Urine pregnancy test will be performed to assess subject eligibility prior to the first administration of IP, if the initial serum pregnancy test did not already occur within 72 hours of dosing (negative results required for IP administration).
- d Serum pregnancy testing during the 80-week Active Treatment Extension Phase occurs every 4 weeks for females of child bearing potential.
- e HRCT used to qualify subjects for inclusion can be performed between Visits 1 and 2, inclusive, or can utilize historical HRCT images (within 18 months of randomization) which still require review by a central reader. For sites subject to regulatory restrictions that do not permit HRCT within this time period, a previous HRCT scan is permissible if the scan is deemed sufficient for centralized review.

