Additional instructions can be found in the electronic case report form (CRF) Completion Guidelines.

- Washout of all disallowed therapies defined in Sections 4.3 and 8.2 if required should commence after the informed consent is signed on the initial day of Screening (Visit 1).
- Complete Physical Examination: Complete physical examinations will include evaluation of the skin, nasal cavities, eyes and ears, respiratory, cardiovascular, abdominal, neurological, lymphatic, and musculoskeletal systems. Gynecological, urogenital and rectal examinations will not be performed unless for cause.
- Vital Signs, Height and Weight: Vital signs, including body temperature, pulse rate, respiration rate, and seated blood pressure will be taken. Height and weight (to be done in street clothes, no shoes) will also be measured and recorded.
- 12-lead electrocardiogram (ECG): All ECG recordings will be manually over-read on an ongoing basis by a cardiologist at the core ECG laboratory for QT measurement and QTc calculation using Fridericia's formula (QTcF). The central cardiologist will interpret all ECGs with respect to PR interval, QRS duration, heart rate and R-R interval, QT and QTcF intervals and for arrhythmia, ischemia or any relevant finding. Details regarding the ECG recordings are described in a separate manual.
- Spirometry: Spirometry for FVC (volume of air that can forcibly be blown out after full inspiration) and FEV1 (maximum volume of air that can forcibly be blown out in the first second during the FVC maneuver) will be performed at prespecified times. Sites are required to use the spirometry equipment provided by the Sponsor. Spirometers must meet the American Thoracic Society/European Respiratory Society (ATS/ERS) criteria (Miller, 2005).

For each subject, all subsequent pulmonary function testing should start at approximately the same time of the day (in the morning with  $\pm 1$  hour maximum difference; time will be recorded). Subjects must refrain from strenuous activity at least 12 hours prior to testing.

Details of the procedure will be described in a separate manual.

DLCO: The DLCO will be measured at prespecified times. DLCO will be measured after the spirometry testing is completed. DLCO equipment will be calibrated centrally to meet ATS/ERS criteria (MacIntyre, 2005). The same tester should be employed during the study. Details of the procedure will be described in a separate manual.

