**Note:**

- *For purposes of study eligibility, inclusion and exclusion criteria/results should be reviewed again prior to randomization (Baseline [Visit 2]) to ensure the subject continues to meet criteria for entry into the study. Additionally, FVC must be repeated at the Baseline (Visit 2) and should be the first assessment done at that visit.*
- *If the subject does not receive IP within 8 weeks after Screening (Visit 1), the subject must be screen failed, and all screening assessments with the exception of*

*the HRCT, if previously done, must be repeated. Details on how to handle screen failures will be described in the CRF operations manual.*

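### The primary MMRM adjusts for the Visit 2 FVC reading only; adding the Screening reading the trial already collects would buy a little precision at almost no cost

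*Combined protocol and SAP*

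**What the plan says.** Section 9.6.1 models percent predicted FVC at the post-baseline visits up to Week 24. The fixed effects are dose, time, current SOC and interactions, prior pirfenidone or nintedanib exposure, "and Baseline percent predicted FVC value as fixed effects covariates". Footnote a of Table 5 defines the term: "The Baseline value is defined as the last assessment prior to or on the date of the first dose of IP in the study". For FVC this is the Visit 2 reading, because the note closing Section 6.1 says "FVC must be repeated at the Baseline (Visit 2) and should be the first assessment done at that visit".

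The earlier reading comes from Screening. Inclusion Criterion 8 (Section 4.2.1) sets percent predicted FVC limits of 45% to 95% "at Screening confirmed by centralized review". Criterion 9 requires the change in FVC (mL) "between Screening and Day 1 less than a 10% relative difference". On equipment, Section 6.1 states: "Sites are required to use the spirometry equipment provided by the Sponsor". The two readings can be up to 8 weeks apart (Section 3.2: "The study will consist of an up to 8-week Screening Phase"). In the text supplied, Screening FVC serves eligibility only; nothing averages it into Baseline or enters it in a model.

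**The concern.** A single spirometry reading carries measurement error. The error in the Visit 2 reading is shared by all of that subject's changes from Baseline, so further post-baseline visits do not average it out. With complete data the Week 24 contrast from the MMRM is essentially a Week 24 ANCOVA on Visit 2 FVC. Adjusting for the noisy value removes little of its own error when subjects differ widely in FVC, because the fitted slope is then close to 1.

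The Screening reading carries separate information about the subject's true starting level. Using it would narrow the intervals. That is relevant here because Section 9.3 states the primary objective as estimating the effect, Section 9.6.1 treats the intervals and p-values as descriptive, and planned power is only 75%.

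**Working it through.** **1. Reproduce the plan's power.** Inputs from Section 9.3: 55 per arm, difference 2.2, SD 5, two-sided alpha 0.1. The blended effect is 0.55 × 3 + 0.45 × 1.3 = 2.24, consistent with 2.2. The noncentrality is 2.2 / (5 × √(2/55)) = 2.2 / 0.953 = 2.31. The noncentral t distribution gives 74.2% and the normal approximation 74.6%. The stated 75% reproduces.

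**2. Assumptions not in the documents.** Single-reading error SD σe from 0.5 to 3 percentage points; SD of true drift from Screening to Day 1, σd, from 0.5 to 2.5; between-subject SD 13 around a mean of 70; drift independent of later change. The SD of change before the eligibility rules is held at the plan's 5, so 25 = (variance of true change) + 2σe².

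**3. Closed form, before eligibility limits.** Visit 2 FVC measures the Day 1 level with error variance σe². Screening FVC measures it with σe² + σd². The best weighted combination has variance σe²(σe² + σd²) / (2σe² + σd²). When between-subject spread is large, the proportional saving in residual variance is therefore about

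σe⁴ / [25 × (2σe² + σd²)].

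- σe = 1, σd = 1: 1 / (25 × 3) = 1.3%
- σe = 2, σd = 1: 16 / (25 × 9) = 7.1%
- σe = 2, σd = 2.5: 16 / (25 × 14.25) = 4.5%
- σe = 3, σd = 0.5: 81 / (25 × 18.25) = 17.8%

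**4. With the eligibility rules applied.** The 45% to 95% limits and the 10% agreement rule remove the most discordant pairs, and with them part of the gain. Simulating subjects under both rules, and comparing a Week 24 regression on Visit 2 plus Screening FVC with one on Visit 2 alone, gives the table below. Power uses SD 5 multiplied by the square root of the variance ratio.

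| Error SD | Variance saved, drift SD 0.5 to 2.5 | Power (74.2% without Screening FVC) |
|---|---|---|
| 0.5 | below 0.5% | 74.2% to 74.3% |
| 1 | 1.7% to 0.4% | 74.8% to 74.3% |
| 1.5 | 4.0% to 1.4% | 75.7% to 74.7% |
| 2 | 6.6% to 3.0% | 76.7% to 75.3% |
| 3 | 11% to 6.6% | 78.5% to 76.7% |

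At the top of the range the variance ratio is about 0.888: the SD becomes 5 × √0.888 = 4.71, the noncentrality 2.2 / (4.71 × √(2/55)) = 2.45, and power 78.5%.

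**5. Effect on the interval.** For drift SD 0 to 2, the 95% half-width for one dose against placebo goes from 1.87 to 1.85–1.86 points at error SD 1, from 1.86 to 1.79–1.82 at error SD 2, and from 1.79 to 1.69–1.72 at error SD 3.

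**The case against.** The strongest reply is that nothing here is an error. A baseline-adjusted MMRM with one baseline value is conventional and valid. A reader might infer that measurement error in the covariate biases the treatment comparison, or that the 75% power is overstated. Neither follows. Randomization makes baseline error independent of arm, and the power figure is an unadjusted t-test with SD 5 that does not depend on this choice. This part of the reply stands in full.

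The second reply concerns size. A reader might infer a guaranteed gain of several percent. The documents give no FVC repeatability figure, and at error SD 0.5 to 1 the gain is between nothing and about 2% of variance. Larger drift over a screening period of up to 8 weeks also erodes it. The 11% end needs error SD 3, which makes measurement error 2 × 9 = 18 of the 25 units of change variance (72%) and has about 10% to 14% of otherwise eligible subjects failing Criterion 9 (drift SD 0 to 2). This stands too: the size must be given as a range starting near zero.

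Third, central review is stated for the Screening value, and no corresponding statement was found for Visit 2, so equal quality control of the two readings should not be assumed.

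Fourth, Section 9.1 leaves detail to a separate SAP. That helps only in part, because Section 9.6.1 already names the covariates and Screening FVC is not among them. Finally, interacting each baseline value with all seven post-baseline visits (Weeks 1, 4, 8, 12, 16, 20 and 24) would use up to 14 coefficients, and the calculation above does not test whether the interactions help.

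**Conclusion.** The point holds as a small, nearly free gain in efficiency. The primary analysis is valid and unbiased as written and the sample size statement is sound. Under the assumed ranges, the omission forgoes about 0% to 11% of Week 24 residual variance, with about 3% to 7% at error SD 2; power would go from 74.2% to between 74.2% and 78.5%. The direction is secure: a second pre-treatment covariate cannot raise the large-sample residual variance, and it lowered it in every scenario run. The size is not secure, because it rests on an error SD and a drift SD that the documents do not supply. The calculation also assumes complete data and drift unrelated to later decline. No conclusion of the trial is likely to turn on this alone.

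**What to change.** Before unblinding, add to Section 9.6.1 that Screening percent predicted FVC enters the MMRM as a second covariate beside the Visit 2 Baseline value. Keep change from Baseline measured from Visit 2. A covariate is safer than averaging the two readings, because the Screening value was used for selection and may be up to 8 weeks older; the model then sets its weight. Make the same addition, with Screening FVC in mL, to the MMRM for FVC under Section 9.6.2.1. An interaction of Screening FVC with time is optional; it raises that term's cost from one coefficient to seven.

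The cost is one sentence per model and a few degrees of freedom with about 165 subjects. No new data, visits or patients are needed. Screening-to-Visit 2 agreement in the pooled blinded data would give the sponsor a rough idea of the likely gain.
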